6.2.1.4.4.1. The thymus recipient blood sample for DNA must be obtained prior to transplantation.

6.2.1.4.4.2. The thymus recipient buccal sample for DNA must be obtained prior to transplantation. The buccal sample is compared to the DNA isolated from purified recipient T cells and maternal DNA prior to the transplant to confirm that the recipient circulating T cells are genetically recipient. This also rules out the presence of T cells from graft versus host disease from an unirradiated blood transfusion.

6.2.1.4.4.3. If maternal sample is not available,

6.2.1.4.4.3.1. High resolution HLA typing will be done on isolated T cells to test for the presence of a 3rd haplotype.

6.2.1.4.4.3.2. Alternatively in male recipients and in male atypical subjects, cytogenetic studies on isolated T cells may be done for XX versus XY chromosomes.

6.2.1.4.5. T Cell Chimerism.

6.2.1.4.5.1. T cell chimerism is done prior to thymus transplantation if there are sufficient T cells.

6.2.1.4.6. Serum is stored prior to transplantation in the event that a serum factor may be found to correlate with athymia in the future.

6.2.1.4.7. Serum Immunoglobulins.

6.2.1.4.7.1. Serum immunoglobulins should be measured monthly prior to transplantation.

6.2.1.4.8. Flow cytometry is done to assess T, B, and NK numbers and phenotypes.

6.2.1.4.8.1. This is done as per inclusion criteria.

6.2.1.4.9. PHA proliferation response. The ability of peripheral blood mononuclear cells (PBMC) to proliferate in response to *in vitro* exposure to PHA.

6.2.1.4.9.1. This is done as per inclusion criteria.

6.2.1.4.10. TRECs.

6.2.1.4.10.1. No requirement for testing.

6.2.1.4.10.2. Newborn screening or other TREC data, if available, will be recorded.

6.2.1.4.11. Flow cytometry for TCRBV repertoire.

6.2.1.4.11.1. This is done prior to transplantation if there are sufficient T cells.

6.2.1.4.11.2. If there is an increase in T cell numbers or activation status, this assay may be repeated at the discretion of the PI.

6.2.1.5. Immunosuppression.

6.2.1.5.1. Rabbit Anti-Thymocyte Globulin (RATGAM).

6.2.1.5.1.1. Dose.

6.2.1.5.1.1.1. Three doses of 2 mg/kg/dose IV. Each dose given over approximately 12 hours.

6.2.1.5.1.1.2. This dose may be modified as medically indicated.

6.2.1.5.1.2. Administration.

6.2.1.5.1.2.1. RATGAM is usually given on days -5, -4, and -3 (relative to thymus transplantation). Days -2 and -1 are usually rest days.

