6.2.1.5.1.2.2. The rabbit anti-thymocyte globulin is started at 0.125 ml/kg/hr, after 60 minutes the rate is increased to 0.25 ml/kg/hr, at 120 minutes it is increased to 0.35 ml/kg/hr and the rate is left at this rate for the rest of the infusion. Note rabbit anti-thymocyte

globulin is reconstituted at 0.5 mg/ml in normal saline.

- If there are adverse reactions with an infusion, such as fever, rash, and/or hypoxia, the rate of rabbit anti-thymocyte globulin administration is decreased per Intensive Care Unit (ICU)/Bone Marrow Transplant Unit (BMTU) guidelines. An example would be to halve the rate.
- Hypersensitivity/anaphylactic reactions will be addressed in accordance with hospital policy ICU/BMTU. The infusion will be stopped temporarily and necessary clinical interventions will be performed per hospital policy to stabilize the subject. Once the reaction has been controlled, the infusion will be resumed at a tolerable rate as directed by the subject's attending physician.

6.2.1.5.1.2.3. The timing of the rabbit anti-thymocyte globulin and days of rest can be modified per the Principal Investigator. Other arrangements of treatment and rest days are permissible as long as the subject receives 3 doses of rabbit anti-thymocyte globulin. The changes are usually due to the subject's medical condition.

6.2.1.5.1.2.4. The thymus transplant must be done within 7 days of completion of the last dose of RATGAM.

- If the transplant is to occur after 7 days from the last dose of RATGAM, a T cell count will be repeated:
 - ⇒ If the T cell count is $<50/\text{mm}^3$, no more RATGAM will be administered
 - ⇒ If the T cell count is $>50/\text{mm}^3$, RATGAM will be repeated at the same schedule and dose as the initial infusion.

6.2.1.5.1.3. Rabbit Anti-Thymocyte Globulin Associated Medications.

6.2.1.5.1.3.1. Methylprednisolone.

6.2.1.5.1.3.1.1. Dose.

- A dose of 2 mg/kg IV is given approximately 4 hours prior to the first dose of rabbit anti-thymocyte globulin.
- A dose of 2 mg/kg/day in divided doses every 6 hours (0.5 mg/kg every 6 hours IV) is given during the administration of rabbit anti-thymocyte globulin prior to transplantation.
 - This dose of steroids continues with every 6 hour dosing for 24 hours after the last dose of rabbit anti-thymocyte globulin is finished.

6.2.1.5.1.3.1.2. For Group 2, methylprednisolone is stopped 24 hours after the last dose of RATGAM ends.

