8.1.2.11.1.1. Rabbit anti-thymocyte globulin can be associated with fever, chills, low white blood cell counts, low platelets, pain, headache, abdominal pain, diarrhea, nausea, alterations in blood pressure, abnormal clotting, swelling, difficulty breathing, high potassium levels, and high heart rate. Many of the side effects are a result of killing the T cells. Rabbit anti-thymocyte globulin is made from animal serum. Individuals treated with animal serum are at risk of serum sickness approximately 1 week later. Serum sickness symptoms include fever, rash, and elevated liver enzymes. There may be other unknown risks of rabbit anti-thymocyte globulin. To try to prevent side effects from the rabbit anti-thymocyte globulin, the subject is treated with 3 doses of acetaminophen, 3 doses of diphenhydramine, and methylprednisolone. These medicines are started 15 minutes to 4 hours (as per protocol) prior to the rabbit anti-thymocyte globulin. The acetaminophen and diphenhydramine will be repeated with each dose of rabbit anti-thymocyte globulin; the steroid will be continued until 24 hours after the last rabbit anti-thymocyte globulin dose.

8.1.2.11.2. Cyclosporine.

8.1.2.11.2.1. There are a number of likely side effects from cyclosporine.

- Cyclosporine can affect the pancreas, liver, kidneys and decrease kidney function. This will be monitored by checking cyclosporine levels, blood studies of pancreatic function, liver function, kidney function, and urine examinations. Abnormalities in the pancreas, liver or kidney will result in reducing cyclosporine doses.
- Cyclosporine can cause low magnesium levels and high potassium.
- Cyclosporine can cause increases in blood pressure. This usually is mild or moderate but may persist. Blood pressure will be monitored daily during the inpatient hospitalization and after discharge at least every 2 weeks. Medication may be given to lower the blood pressure.
- Cyclosporine can result in excessive body hair.
- Cyclosporine can increase risk of infection in people born with thymuses, but this risk does not apply to complete DiGeorge anomaly because these pediatric patients are already at risk for infection. Cyclosporine does not change this risk.
- Infrequently cyclosporine can result in seizures (less than 1 in

- 20). More frequently, a tremor (trembling or quivering) can develop.

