5.5 Baseline and Demographic Characteristics

All baseline and demographic characteristics will be summarised for each protocol. This will include age on day of transplantation (in days), sex, race, ethnicity, height, weight, BSA, and relevant medical history. Baseline is defined as the last value obtained prior to thymus transplantation. For subjects who received RATGAM prior to the transplantation, baseline for flow cytometry, proliferation, and PHA values will be defined as the last value obtained prior to the initiation of the first dose of RATGAM. If multiple values are recorded on the same day, the average of all measurements taken on that day will be used as the baseline value.

Notes:

- BSA will be calculated using Haycock's formula:
 - $BSA (m^2) = 0.024265 \times (weight[kg])^{0.5378} \times (height[cm])^{0.3964}$
- Medical history will be coded according to MedDRA version 19.1.
- Relevant medical histories are all medical histories recorded in the CRF.
- Any duration [days] = end day – onset day + 1

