5.8.3 Vital signs

A summary of vital signs for observed value and change from baseline over time will be produced using the safety analysis windows given in Table 5.3.2.1. All data will be listed.

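### In RATGAM recipients the SAP's haematology baseline, and plausibly the vital-sign baseline, usually falls during or after RATGAM, because the pre-RATGAM rule covers only flow cytometry, proliferation and PHA

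*SAP*

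**What the plan says.** SAP 5.5 sets a general rule: "Baseline is defined as the last value obtained prior to thymus transplantation". It then makes one exception. For subjects who received RATGAM, "baseline for flow cytometry, proliferation, and PHA values will be defined as the last value obtained prior to the initiation of the first dose of" that drug. No other parameter is named in the exception.

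SAP 5.8.2 summarises the safety laboratories (haematology, endocrine, FEN, liver) both as values at each visit and as change from baseline. SAP 5.8.3 does the same for vital signs: "A summary of vital signs for observed value and change from baseline over time will be produced".

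Protocol 6.2.1.5.1.2.1 places the three RATGAM doses usually on days -5, -4 and -3. Protocol 6.2.1.5.1.2.4 adds: "The thymus transplant must be done within 7 days of completion of the last dose of RATGAM". Methylprednisolone starts about four hours before the first dose and, under Protocol 6.2.1.5.1.3.1.1, "This dose of steroids continues with every 6 hour dosing for 24 hours after the last dose of rabbit anti-thymocyte globulin is finished". Protocol 8.1.2.11.1.1 lists among the effects of RATGAM "low white blood cell counts, low platelets", and also altered blood pressure, high potassium, high heart rate and, through serum sickness, raised liver enzymes.

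**The concern.** The exception shows that the SAP authors knew a value taken after RATGAM is a poor starting point. It covers only the T cell assays, although the protocol says the same drug can lower white cells and platelets and alter blood pressure and heart rate. If the last pre-transplant CBC is taken during or after the course, a platelet count that is only returning to its former level is tabulated as a rise after the graft. A true fall is measured from an already lowered start and looks smaller.

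These are not peripheral measures. Protocol 6.2.1.8.3.1.2 treats haemoglobin, platelets and neutrophils as the most important counts for detecting immune-based events, and Protocol Table 2 reports related thrombocytopenia in 11 of 93 subjects and hypertension in 15 of 93.

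The tables would not reveal the problem. SAP 5.3.2 has a single pre-transplant window, open-ended in the past and closing at day -1, and the SAP calls for no split by treatment group. Group 1 receives no RATGAM, so baselines of different kinds would sit in one column.

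**Working it through.** The documents state no figure for this point, so there is none to reproduce. The check asks how often the last routine pre-transplant sample falls after the first RATGAM dose, and what that does to the change column.

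**Inputs**
- Usual time from first dose to transplant: first dose on day -5, so W = 5 days (Protocol 6.2.1.5.1.2.1).
- Longest planned time: three daily doses with transplant 7 days after the last, so W = 2 + 7 = 9 days (Protocol 6.2.1.5.1.2.4).
- Pre-transplant CBC: weekly, I = 7 days (Protocol 6.2.1.2.4.1.1).
- Electrolytes, minerals and liver tests: at least monthly, I = 30 days taken as a month (Protocol 6.2.1.2.4.2 to 6.2.1.2.4.4).
- Thyroid tests: at least once within two months, I = 60 days (Protocol 6.2.1.2.5.4).

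**Formula.** With routine samples only, at a random phase relative to RATGAM, P(last sample after first dose) = min(1, W / I).

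| Test | W = 5 | W = 9 |
|---|---|---|
| CBC | 5/7 = 71% | 9/7, capped at 100% |
| Chemistry, liver | 5/30 = 17% | 9/30 = 30% |
| Thyroid | 5/60 = 8% | 9/60 = 15% |

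Samples taken as medically indicated would raise these shares; the documents do not say by how much.

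**Vital signs.** The pre-transplant screening text gives no routine interval, so no share is computed. Protocol 8.1.1.1 has inpatients monitored daily, and Protocol 8.1.2.11.2.1 has blood pressure checked daily in inpatients on cyclosporine. A last value after the RATGAM course is therefore plausible, but not required by the schedule.

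**Effect on the change column.** Let P be the pre-RATGAM value, d the drop still present at the last pre-transplant sample, and F the value at a later visit. The tabulated change is F - (P - d) = (F - P) + d. It exceeds the change from the pre-RATGAM level by d. Averaged over RATGAM recipients, the shift is the share with a late baseline times the mean d among those subjects. The documents give no value for d. Purely for scale, an assumed platelet drop of 50 to 150 x10^9/L would give 0.714 x 50 = 36 at the low end and 1.00 x 150 = 150 at the high end, per RATGAM recipient. That range is an assumption, not a finding.

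**Who is affected.** Protocol 2.2.2.3.1 counts 55 RATGAM recipients among the 93 EAS-cDGA subjects, 55/93 = 59%. This is a programme-wide figure at August 2020; the share within study 25966 is not given.

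**Internal inconsistency.** SAP 5.8.2.2 lists the absolute lymphocyte count under Flow Cytometry, so it takes the pre-RATGAM baseline. SAP 5.8.2.1 lists lymphocytes under Hematology, so they take the last pre-transplant value. In the same RATGAM recipient, two closely related measures can show different changes.

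**The case against.** The strongest defence is that the study treatment is the graft (SAP 4.2), and the last value before the graft is the natural reference for change after it. The flow exception has its own reason: RATGAM kills T cells, which those assays count or stimulate. This has force: which reference to use is partly a choice. But the SAP does not say which change it means, and recovery from RATGAM after surgery would still appear in the change column. The last pre-transplant value therefore does not isolate the graft effect.

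Other objections stand and limit the point:

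- A reader might infer that every safety change from baseline is distorted. The documents do not support that. On the minimum schedule most chemistry, liver and thyroid baselines precede RATGAM, Group 1 receives none, and adverse events are counts, not changes.
- A reader might infer that cytopenias would be missed. They would not: SAP 5.8.2 also shows the observed values, flags out-of-range results in the listings and reports clinically significant findings as adverse events, and SAP 5.8.1.2 makes autoimmune disease an event of special interest.
- A reader might take a pre-RATGAM value as an untreated state. In Groups 3 and 4 cyclosporine starts at least 7 days before RATGAM (Protocol 6.2.1.5.3.2.2), and cyclosporine and steroids may start before enrolment (Protocol 4.2.2.5).
- Protocol 6.3.1.6.1 permits alemtuzumab before transplantation, which might suggest a second gap in the flow baseline. Groups 2 to 4 are all assigned three RATGAM doses, and neither document describes a subject given alemtuzumab without RATGAM. That case is hypothetical.
- The change columns are descriptive; no hypothesis test uses them (SAP 3.3).

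**Conclusion.** The point holds for haematology, plausibly for vital signs, and in part for chemistry and liver tests. In RATGAM recipients the last routine CBC falls after the first dose in about 71% to 100% of cases, against 17% to 30% for chemistry and liver tests. These shares assume routine sampling only, random timing, a 30-day month and a 5- to 9-day window.

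The change columns can therefore show recovery from RATGAM as post-transplant change and understate falls in platelets and white cells. That direction rests on the protocol's own list of RATGAM effects. For vital signs the protocol gives no single direction for blood pressure. The size of any shift is not in the documents. The different baselines for the absolute lymphocyte count and lymphocytes follow directly from the SAP text and need no assumption. No test, observed-value summary or adverse-event summary is affected, so this is a correction to descriptive safety tables.

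**What to change.** Amend SAP 5.5 for subjects who received RATGAM:

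1. Define the haematology and vital-sign baseline as the last value before the first RATGAM dose, as already done for flow cytometry.
2. Display the last pre-transplant value, and the change from it, as a separate row. The change across the RATGAM course and the change after the graft are then both visible.
3. Use one baseline for the absolute lymphocyte count and haematology lymphocytes.
4. For chemistry and liver tests, show both references where a pre-RATGAM value exists.
5. List the baseline sampling day relative to the first RATGAM dose, and flag subjects with no pre-RATGAM value.

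The cost is one derived flag and a few table rows, with no new data collection and no change to clinical conduct. The downsides are a slightly older baseline, an occasional missing one, and a reference in Groups 3 and 4 that may still be on cyclosporine or steroids; a table footnote should say so.

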5.6 Concomitant Medication

Medically needed therapies to treat the subject are allowed; however, per protocol this information will not be databased or summarized. Protocol required immunosuppressive therapies and calcium/calcitriol supplementation (parathyroid transplant recipients only) will be summarized and listed.

5.7 Efficacy / Primary and Secondary Analysis

5.7.1 Method of analysis for primary endpoints

Because the profound immune deficiency of athymia leads to death from infection usually before the age of 2 years, survival was the primary endpoint of the clinical studies. The Kaplan-Meier

CONFIDENTIAL

estimates of survival at Year 1 and Year 2 will be presented with number at risk, number with events, and estimated survival probability. The Kaplan-Meier survival tables (Table 14.2.1.2.1 and Table 14.2.1.2.14) and the associated figures (Figure 14.2.1.2.1 and Figure 14.2.1.2.14) will be limited to a five-year duration.

5.7.2 Methods of analysis for secondary outcomes

Immune outcomes and dose effect are assessed after thymus transplantation by examining biopsies of the allografts by immunohistochemistry; flow cytometry; assessing variability of the T cell receptor beta gene variable (TCR β V) region; assessing T cell proliferative responses and measuring B cell antibody responses to antigens. Descriptive summaries will be provided at Year 1, and if available at Year 2.

5.8 Safety Analysis

Safety assessments were gathered for at least two years in all studies. Summaries of safety events will include events happening within two years of transplantation. All reported events, regardless of time of onset, will be included in the listings.

5.8.1 Adverse events

Adverse events and serious adverse events will be summarised separately by presenting the number and percentage of subjects having any event, having a related event, having an event in each MedDRA system organ class and preferred term, having each individual event and the severity, relationship and outcome of each event. Number of events is also presented. Missing severity, relationship or outcome will be classed as unknown.

A subject with more than one occurrence of the same adverse event in a particular system organ class will be counted only once in the total of those experiencing adverse events in that particular system organ class. If a subject experiences the same adverse event at more than one severity, or with more than one relationship to study drug, the most severe rating or the stronger causal relationship to study drug will be given precedence. Any missing severity, causality, or outcome will not be imputed and classed as unknown.

Summaries classifying both events according to severity and relationship will be presented.

Related events are defined as events that are definitely, probably, or possibly related to study treatment or with an unknown relationship.

Non-infection-related AEs and SAEs were graded (Grades 1-5) according to the National Cancer Institute's Common Terminology Criteria for Adverse Events (CTCAE). CTCAE version 3.0 was used for studies 668-1/2, 884/884.1, 931, 932, 950/950.1, 25966, 735, and 33170. CTCAE version 4.0 was used for Study 51692. The severity AEs will be used as collected, thus for the analysis of AEs of Grade ≥ 3 will be based on the CTCAE version used in the respective protocol.

CONFIDENTIAL

Infection-related AEs were evaluated using either CTCAE criteria or criteria defined in the Blood and Marrow Transplant Clinical Trials Network (BMTCTN) definitions of infection severity. Infection-related AEs with BMTCTN severity \geq severe will be included in the analysis of AEs of Grade \geq 3. For the purposes of summarization, all AEs including infection related AEs will be included in AE summary tables unless otherwise specified.

5.8.1.1 Subsets

- Adverse events will be presented by system organ class and preferred term
- Serious adverse events will be presented by system organ class and preferred term
 - Related serious adverse events will be presented by system organ class and preferred term.
- Deaths will be listed

All other information collected (e.g., action taken) will be listed as appropriate.

All adverse events will be included in the adverse and serious adverse event summaries.

Notes:

- Tables presented will contain both counts of subjects and events. Subjects who have multiple events in the same system organ class and preferred term will be counted only once in the subject counts.
- AEs coded using MedDRA version 19.1.

5.8.1.2 Adverse events of special interest

Adverse events of special interest (AESI) will be summarized by system organ class and preferred term, and will include infection-related AEs, cancers, autoimmune diseases, GVHD, rashes, and granulomas.

5.8.2 Safety and Efficacy Laboratory findings

Results from the following laboratory parameters (5.8.2.1 and 5.8.2.2) will be summarised using the value at each visit and change from baseline at each visit.

Categorical and numeric variables will be presented separately.

Clinically significant treatment-emergent laboratory findings will be summarised as adverse events.

Notes:

- All results outside predefined normal ranges will be flagged in the data listings.

CONFIDENTIAL

Sponsor:	Enzyvant Therapeutics GmbH	Program:	RVT-802
----------	----------------------------	----------	---------

- Repeat laboratory results within a visit will not be used in any summary calculations. Unscheduled (those obtained outside of the safety analysis windows defined in Section 4.3.2) and repeat results will be listed only.
- Any other laboratory results will be listed only.

5.8.2.1 Clinical Safety Laboratories

Hematology:

Hemoglobin, Hematocrit, Platelet Count, RBC, WBC, Neutrophils, Bands, Lymphocytes, Monocytes, Eosinophils, Basophils, Atypical Lymphocytes, and other Myelocytes.

Endocrine:

Calcium, Ionized Calcium, Magnesium, Phosphorus, Urine Calcium, Urine Creatinine, Ratio, T4, Free T4, TSH, iPTH, Anti-TGB, and Anti-TPO.

FEN:

Sodium, Potassium, Chloride, CO₂ (Bicarbonate), Glucose, BUN, and Creatinine.

Liver Function:

AST, ALT, Alkaline Phosphatase, Bilirubin, LDH, Lipase, Amylase, Albumin, Total Protein, GGT, and Triglycerides.

5.8.2.2 Clinical Efficacy Laboratories

Serum Immunoglobulins and Isohemagglutinins:

IgG, IgA, IgM, IgG, Anti-A, and Anti-B.

Flow Cytometry:

Percentage of ALC, CD3, CD4, CD8, DB Neg, TCR $\alpha\beta$, TCR $\gamma\delta$, B, NK, Naïve CD3, Naïve CD4, and Naïve CD8 cells.

Number of ALC, CD3, CD4, CD8, DB Neg, TCR $\alpha\beta$, TCR $\gamma\delta$, B, NK, Naïve CD3, Naïve CD4, and Naïve CD8 cells.

TCR Flow:

VB1, VB2, VB3, VB4, VB5.1, VB5.2, VB5.3, VB7.1, VB7.2, VB7, VB8, Vb8.1/8.2, Vb9, VB11, VB12, VB13.1, VB13.2, VB13.6, VB14, VB16, VB17, VB18, Vb20, VB21.3, VB22, and VB23.

Proliferation Assay:

PT CONA, PT CONA BKG, CONTROL CONA, CONTROL CONA BKG, PT SOL CD3, PT SOL CD3 BKG, PT INSOL CD3 PT INSOL BKG, PT IMMOB CD3, PT IMMOB CD3 BKG, CONTROL SOL CD3, CONTROL SOL CD3 BKG CONTROL IMMOB CD3, CONTROL

CONFIDENTIAL

Sponsor:	Enzyvant Therapeutics GmbH	Program:	RVT-802
----------	----------------------------	----------	---------

IMMOB CD3 BKG, PT TT, PT TT BKG (PT AG BKG), CONTROL TT, CONTROL TT BKG (CTRL AG BKG), PT CANDIDA, PT CANDIDA BKG, CONTROL CANDIDA, and CONTROL CANDIDA BKG.

